Abbreviations: ADA=anti-drug antibody; ClinRO=clinician-reported outcome; BSA=Body Surface Area; C-SSRS=Columbia-Suicide Severity Rating Scale; DLQI=Dermatological Life Quality Index; DNA=deoxyribonucleic acid; ECG=electrocardiogram; f-PGA=Fingernail Physician's Global Assessment; GenPs-SFQ=Genital Psoriasis Sexual Frequency Questionnaire; hs-CRP=High sensitivity C-reactive protein; HIV=human immunodeficiency virus; ICF=informed consent form; IGA=Investigator Global Assessment; IGRA=Interferon gamma release assay; LTE=long-term extension; NAPSI=Nail Psoriasis Area and Severity Index; PASI=Psoriasis Area and Severity Index; PBMC= peripheral blood mononuclear cells; PGI-C=Patient Global Assessment-Change; PGI-S=Patient Global Assessment – Severity; PK=pharmacokinetic(s); PRO=patient-reported outcome; PROMIS-29=Patient Reported Outcomes Measurement Information System-29; PSSD=Psoriasis Symptom and Sign Diary; SoA=Schedule of Activities; s-PGA=Static Physician's Global Assessment; ss-IGA=Scalp Specific Investigator Global Assessment; TB=tuberculosis; TSQM-9=Treatment Satisfaction Questionnaire for Medications

Footnotes:

- a. For participants who DO NOT enter the LTE protocol, a Final Safety Follow-up Visit (ie, Week 20) will be conducted approximately 4 weeks after the last administration of study intervention. Participants who enter the LTE will enter at or after the Week 16 visit.
- b. Participants who terminate study intervention early should have an Early Termination Visit approximately 4 weeks after their last administration of study intervention.
- c. Length of time between Week 1 and Week 2 visits must not exceed 10 days.
- d. At all visits where study intervention will be dispensed, all study procedures and evaluations are to be completed before study intervention is dispensed.
- e. At Week 0, all blood samples should be collected prior to study intervention administration and the date and time of collection should be recorded in the source document. At all other study visits where applicable, the date and time of the two previously administered doses and the date and time of the samples should be recorded as instructed in the study manual.

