Under normal circumstances, the blind should not be broken until all participants have completed the study and the database is finalized. The investigator may, in an emergency, determine the identity of the intervention by contacting the IWRS. While the responsibility to break the intervention code in emergency situations resides solely with the investigator, it is recommended that the investigator contact the sponsor or its designee if possible, to discuss the particular situation, before breaking the blind. Telephone contact with the sponsor or its designee will be available 24 hours per day, 7 days per week. In the event the blind is broken, the sponsor must be informed as soon as possible. The date, time, and reason for the unblinding must be documented by the IWRS and in the source document. The documentation received from the IWRS indicating the code break must be retained with the participant's source documents in a secure manner.

Participants who have had their intervention assignment unblinded should continue to return for scheduled evaluations.

In general, randomization codes will be disclosed fully only if the study is completed, and the clinical database is closed. However, for the interim analyses (Section 9.5), the randomization codes and, if required, the translation of randomization codes into intervention and control groups

will be disclosed to those authorized (ie, internal independent IAC) and only for those participants included in the interim analysis.

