6.6. Continued Access to Study Intervention After the End of the Study

Participants will be instructed that study intervention will not be made available to them after they have discontinued study intervention for any reason outlined in Section 7.1 and that they should return to their primary physician to determine standard of care.

At the end of study treatment (Week 16), participants who meet all eligibility requirements outlined in the LTE protocol, (77242113PSO2002), will be offered the opportunity to enter the 36-week treatment LTE study. Further details about the LTE study design will be outlined in a separate protocol (772424113PSO2002).

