6.8. Concomitant Therapy

Modification of an effective preexisting therapy should not be made for the explicit purpose of entering a participant into the study. Concomitant therapies must be recorded throughout the study beginning with start of the first dose of study intervention to 4 weeks after the last dose of study intervention.

All therapies (prescription or over-the-counter medications) different from the study intervention must be recorded in the eCRF. Every effort should be made to keep participants on stable concomitant medications. If a medication is temporarily discontinued because of abnormal laboratory values, side effects, concurrent illness, or the performance of a procedure, the change and reason for it should be clearly documented in the participant's medical records.

Any questions regarding treatment with concomitant medication during the study should be directed to the medical monitor.

Prohibited Therapy

All experimental therapies or new investigational interventions (except for JNJ-77242113), including therapies for psoriasis or other conditions, must be discontinued prior to the first administration of study intervention per Exclusion Criteria (Section 5.2) and remain prohibited during the study. For guidance regarding the COVID-19 vaccine see Section 6.8.1.

If a prohibited therapy is administered during the active treatment phase (ie, Week 0 to Week 16), the medical monitor should be notified, and the participant may be required to discontinue from the study treatment per medical monitor's discretion. If a prohibited therapy is initiated during the safety follow-up period, the participant should still complete his or her final study visit, and the medication should be recorded as a concomitant medication.

The sponsor must be notified in advance (or as soon as possible thereafter) of any instances in which prohibited therapies are administered.

Psoriasis Concomitant Medications

Topical Therapy

Topical therapies that could affect psoriasis or the PASI/IGA evaluation (eg, corticosteroids, tar, anthralin, calcipotriene, tazarotene, methoxsalen, pimecrolimus, tacrolimus, and traditional Taiwanese, Korean, or Chinese medicines) are not permitted during the study. The only allowable concomitant treatments throughout the study are shampoos (containing salicylic acid only) and

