Participants who decide to discontinue study intervention administration for reasons other than those outlined above must be interviewed by the investigator to determine if a specific reason for discontinuing study intervention can be identified. Participants should be explicitly asked about the possible contribution of AEs to their decision to discontinue study intervention; investigators should confirm that any AE information elicited has been documented. If a participant elects to discontinue study intervention due to an AE, the event should be recorded as the reason for study intervention discontinuation, even if the investigator's assessment is that the AE would not require study intervention discontinuation. The reason for study intervention discontinuation must be documented in the eCRF and in source documents. Study intervention assigned to a participant who discontinues may not be assigned to another participant.

A participant will not be automatically withdrawn from the study if he or she must discontinue treatment before the end of the treatment regimen. Participants who discontinue study intervention but do not terminate study participation will continue to return for protocol-specified procedures and evaluations for approximately 4 weeks following the last administration of study intervention. The procedures and evaluations listed for the Early Termination Visit should also be performed approximately 4 weeks after the last administration of study intervention.

All procedures and evaluations must be conducted prior to a participant's withdrawal of consent.

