7.2. Participant Discontinuation/Withdrawal From the Study

A participant will be withdrawn from the study for any of the following reasons:

- Lost to follow-up
- Withdrawal of consent
- The participant is not in compliance with requirements of the study, including prohibitions and restrictions
- Death

When a participant withdraws before study completion, the reason for withdrawal is to be documented in the CRF and in the source document. If the reason for withdrawal from the study is withdrawal of consent, then no additional assessments are allowed.

Withdrawal of Consent

A participant declining to return for scheduled visits does not necessarily constitute withdrawal of consent. Alternate follow-up mechanisms that the participant agreed to when signing the consent form apply (eg, consult with family members, contacting the participant's other physicians, medical records, database searches, use of locator agencies at study completion) as local regulations permit.

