9.4.2.1.1. Estimand

9.4.2.1.1.1. Primary Estimand

The primary estimand (ie, a precise definition of the primary targeted treatment effect) is defined by the following 5 attributes:

Study intervention:

- JNJ-77242113 25 mg QD, 50 mg QD, 25 mg BID, 100 mg QD, and 100 mg BID
- Placebo

Population: adult participants with moderate to severe plaque psoriasis

Variable/endpoint: Response binary variable, where a responder is defined as a participant achieving a PASI 75 response at Week 16 who does not have intercurrent events in categories 1-2 (defined below).

Intercurrent Events (ICEs) and their corresponding strategies

ICEs	Analysis Strategy for Addressing Intercurrent Events
1. Discontinuation of study intervention due to lack of efficacy or due to an AE of worsening of psoriasis	Composite Strategy: Participants with these intercurrent events are considered as PASI 75 non-responders after these events, and prior to Week 16. The occurrence of these intercurrent events is captured in the variable definition.

2. Initiation of a protocol-prohibited medication or therapy during the study that could improve psoriasis	
3. Discontinuation of study intervention for reasons other than ICE 1	Treatment Policy: observed data will be used regardless of whether or not this intercurrent event had occurred.

Note: For participants experiencing multiple ICEs, ICE 2 will override ICE 3.

Population level summary: Difference in the proportions of participants achieving a PASI 75 response at Week 16 between the JNJ-77242113 and placebo intervention groups.

Primary Endpoint Analysis

In the primary efficacy analysis, data from all randomized participants who received at least 1 administration of study intervention will be analyzed according to their assigned treatment group.

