5.3.1.2.1. Primary Estimand (Estimand 1)

The primary estimand, based on the above primary objective, is defined by the following 5 attributes which assess the treatment effects not only based on the variable measurements, but also based on intercurrent events:

Study intervention:

- JNJ77242113 25 mg QD, 50 mg QD, 25 mg BID, 100 mg QD, and 100 mg BID.
- Placebo

Population: adult participants with moderate to severe psoriasis

Variable/endpoint: Binary response variable, where a responder is defined as a participant achieving a PASI75 response at Week 16. A participant with an intercurrent event in categories 1-2 defined below will be considered as a non-responder.

Intercurrent Events (ICEs) and their corresponding strategies.

ICEs	Analysis Strategy for Addressing Intercurrent Events
1. Discontinuation of study intervention due to lack of efficacy, or an AE of worsening of psoriasis prior to Week 16	Composite Strategy: Participants with these intercurrent event are considered as non-responders. The occurrence of these intercurrent events is captured in the variable definition.

2. Initiation of a protocol-prohibited medication or therapy during the study that could improve psoriasis prior to Week 16	
3. Discontinuation of study intervention for reasons other than ICE 1	Treatment Policy: observed data will be used regardless of whether or not this intercurrent event had occurred.

- ICEs 1 and 2 will be handled by the composite strategy, where the occurrence of the ICE will be incorporated into the variable definition. Participants experiencing ICE 1 or 2 will be considered not to have achieved the primary endpoint.

- ICE 3 will be handled using the treatment policy strategy regardless of the intercurrent event.

Note: For participants experiencing multiple ICEs, ICE 2 will override ICE 3.

A list of Participants who experienced ICEs 1-3 will be provided.

Population level summary: Difference in the proportions of participants achieving a PASI 75 responses at Week 16 between the treatment groups.

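### ICE 3 is declared treatment policy, but follow-up ends about 4 weeks after the last dose, so early stoppers have no planned Week 16 PASI and Supplementary Analysis 2 and the MMRM rely on MAR for them

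*Protocol*

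**What the plan says.** **Estimand.** For ICE 3, Protocol 9.4.2.1.1.1 states that "observed data will be used regardless of whether or not this intercurrent event had occurred". SAP 5.3.1.2.1 agrees: "ICE 3 will be handled using the treatment policy strategy regardless of the intercurrent event".

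**Follow-up.** Under Protocol 7.1, those who stop study intervention without leaving the study "will continue to return for protocol-specified procedures and evaluations for approximately 4 weeks following the last administration of study intervention". Footnote b of the Schedule of Activities sets the closing visit at the same time: "Participants who terminate study intervention early should have an Early Termination Visit approximately 4 weeks after their last administration of study intervention". Two narrower provisions point the other way. Section 6.3 says "Participants who have had their intervention assignment unblinded should continue to return for scheduled evaluations", without giving a duration, and Section 8.2.8 encourages continued attendance when dosing is withheld for a tuberculosis work-up. Section 6.6 tells those who stop that "they should return to their primary physician to determine standard of care". Section 6.8 has concomitant therapy recorded "beginning with start of the first dose of study intervention to 4 weeks after the last dose of study intervention".

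**Analysis.** By-visit analyses use nominal visits (SAP 5.1.1), and no rule carries an Early Termination PASI to Week 16. Missing data are then handled in three ways:
- Primary analysis (SAP 5.3.1.2.3): non-response.
- Supplementary Analysis 2, the treatment-policy analysis (SAP 5.3.1.2.5.2): the multiple imputation of Section 5.3.1.2.5.1, built for the hypothetical estimand. Its predictors are treatment group, baseline PASI and PASI 75 status by visit. Section 5.4.1.3.1.1 extends it to PASI 90, PASI 100, IGA 0/1 and IGA 0.
- Continuous secondary endpoints, numbers 5–8 and 12 in SAP 5.4.1.2 (SAP 5.4.1.3.2): no imputation, and an MMRM that assumes missing at random (MAR).

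**The concern.** A treatment-policy strategy needs outcomes after the event. For ICE 3 participants who stop early, the visit rule stops collecting them before Week 16, so the strategy and the planned data do not match.

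The non-response rule settles the matter explicitly and conservatively for the primary endpoint and for the main analyses of the binary secondary endpoints. The other two analyses have no such rule. The imputation model has no term for being off treatment, so for early stoppers Supplementary Analysis 2 drifts towards the hypothetical estimand it is meant to contrast with. The MMRM borrows from participants in the same arm who are mostly still dosing. If response fades after stopping, both overstate the active-placebo difference.

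The gap is somewhat wider than ICE 3. Supplementary Estimand 2 applies treatment policy to ICEs 1–3, so participants who stop early for lack of efficacy fall into it too.

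**Working it through.** **The plan's own power figure.** Protocol 9.2 claims at least 90% power for a 35-point difference with n = 40 per arm and 2-sided 0.05, by a Z-test. With the pooled test, power = Φ{[Δ − 1.96·√(2p̄(1−p̄)/n)] / √[p₁(1−p₁)/n + p₂(1−p₂)/n]}. For 5% v 40% this is Φ[(0.35 − 0.183)/0.0848] = 97.6%, and for 10% v 45% it is 95.4%. The claim is met.

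**Cut-off.** Week 16 is 112 days after the first dose, and 112 − 28 = 84 days, or Week 12.0. Using the 4-day window early, (112 − 4 − 28)/7 = Week 11.4.

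**Share affected.** The documents give no ICE 3 rate or timing. Assume a rate r of 5%, 10% or 15% per arm, spread evenly over 16 weeks. The share of ICE 3 cases with no planned Week 16 PASI is 12/16 = 75%, or (12 − 4/7)/16 = 71% with the window fully used. Per arm that is at most 40 × 0.75r = 1.5, 3.0 or 4.5 participants.

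**Primary analysis.** If both arms lose these cases to non-response, the 35-point difference becomes 35 × (1 − 0.75r):

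| r | Difference | Power, 5% v 40% | Power, 10% v 45% |
|---|---|---|---|
| 5% | 33.7 | 96.9% | 94.2% |
| 10% | 32.4 | 96.0% | 92.9% |
| 15% | 31.1 | 95.0% | 91.4% |

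**Supplementary Analysis 2.** This was simulated with six arms at 6/30/45/55/65/70%, visits at Weeks 1, 2, 4, 8, 12 and 16, data kept to 4 weeks after the last dose, and missing visits imputed in sequence by logistic regression on arm and earlier PASI 75 status (baseline PASI omitted). With no later therapy and no new response after stopping, the overstatement of the 70% v 6% difference, in points, is:

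| Median time to loss of response | r = 5% | r = 10% | r = 15% |
|---|---|---|---|
| 2 weeks | 2.02 | 3.90 | 5.70 |
| 4 weeks | 1.83 | 3.68 | 5.43 |
| 8 weeks | 1.68 | 3.31 | 4.94 |
| 16 weeks | 1.50 | 2.95 | 4.46 |
| no loss | 1.26 | 2.57 | 3.77 |

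The Monte Carlo error is 0.01–0.07. The sampling SE of the difference is √(0.7×0.3/40 + 0.06×0.94/40) = 8.2 points. Two simulations built differently gave 1.4–1.9/2.8–3.8/4.1–5.6 and 1.8–2.2/3.6–4.2/5.5–6.4.

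**Later therapy.** Take r = 10%, and let a fraction q of early stoppers in every arm respond on later therapy by Week 16 (median loss of response 4 or 16 weeks):

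| q | Active-arm bias | Bias in difference |
|---|---|---|
| 20% | +2.1 to +2.5 | 3.3–3.8 |
| 40% | +0.9 to +1.2 | 3.5–3.9 |
| 60% | −0.4 to −0.1 | 3.8–4.1 |

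The active-arm bias vanishes or reverses, but the difference stays overstated because placebo responses on later therapy are missed as well.

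**MMRM of PASI change.** Assumed: baseline PASI 16 (SD 4) or 20 (SD 6), on-drug improvement 60% or 80% v 10% on placebo, half-life of return to placebo level 2–16 weeks, no later therapy, weight stratum omitted. At r = 5/10/15% the difference is overstated by 1.7–2.7%, 3.5–5.6% and 5.4–8.7% of its true size. That is 0.15–0.35, 0.29–0.70 and 0.44–1.03 PASI points, against an SE of 0.7–1.2.

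**The case against.** The best case against giving this weight has five parts.

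- **No decision depends on it.** Success rests on the gMCP-Mod test, which is unaffected. The exposed analyses are supplementary, or secondary with nominal p-values. This holds and limits the severity. Even so, the MMRM is the main analysis for its endpoints.
- **The SAP already separates intercurrent events from missing data and names MAR.** Using whatever is observed and then a stated missing-data rule is not in itself a contradiction. That is fair, but here the visit rule creates the missingness by design, and an analysis labelled treatment policy then fills it mainly from on-treatment data.
- **Not all the bias comes from the 4-week rule.** Some early stoppers also withdraw consent or are lost. Section 7.2 is clear: "If the reason for withdrawal from the study is withdrawal of consent, then no additional assessments are allowed". This stands. If only half of early stoppers can be followed, about half of the bias is removed.
- **Every magnitude is assumed.** That is true, and only PASI change was examined among the continuous endpoints. Even the 5.7-point case is about 0.7 of an SE (5.7/8.2).
- **Concomitant medication is already recorded at each visit** (Section 8.2.5 and the Schedule of Activities), so extending visits would bring most of the recording with them. Largely right. Section 6.8 still ends recording at 4 weeks and would have to be aligned.

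**Conclusion.** The point holds and is worth fixing. For a last dose before about Week 12, the treatment-policy strategy for ICE 3 has no planned Week 16 data behind it. The primary test and the stated power are not threatened. What is exposed is Supplementary Analysis 2 (PASI 75 and four binary secondary endpoints) and the MMRM for the five numbered continuous secondary endpoints.

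In the scenarios examined the bias always favours active treatment but is smaller than one SE. The sizes rest on assumed ICE 3 rates, even timing of stopping and assumed off-drug behaviour, none of which the documents supply. The mismatch itself does not rest on those assumptions.

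**What to change.** **Preferred.** Amend Protocol 7.1 and footnote b of the Schedule of Activities so that participants who stop study intervention but do not withdraw from the study keep the already scheduled efficacy assessments through Week 16, in addition to the visit about 4 weeks after the last dose. In the same amendment, extend concomitant-therapy recording in Section 6.8 to Week 16 for them, so that ICE 2 is still identified and overrides ICE 3, and reconcile the text with Sections 6.3, 8.2.5 and 8.2.8. This concerns data collection only and changes no treatment.

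The two extensions belong together. If PASI alone were extended and 20–60% of early stoppers responded on unrecorded later therapy, 40 × 0.75r × q = 0.3–0.9, 0.6–1.8 or 0.9–2.7 participants per arm (r = 5/10/15%) would count as primary responders instead of ICE 2 cases. This is a worst case, given Section 8.2.5.

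**Cost.** A few extra scheduled visits for at most about 1.5–4.5 participants per arm, and fewer once consent withdrawal and loss to follow-up are allowed for. The amendment is short, but with any consent-form revision it needs ethics committee approval before use (Section 10.3.1).

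**Fallback, wording only.** Keep the ICE 3 row as the estimand. State beside it that early cases without a Week 16 PASI are handled by the non-response rule of SAP 5.3.1.2.3. Do not present Supplementary Analysis 2 as a treatment-policy estimate for participants with no off-treatment Week 16 data, and note the same MAR reliance for the MMRM. This discloses the gap without closing it.

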7.2. Participant Discontinuation/Withdrawal From the Study

A participant will be withdrawn from the study for any of the following reasons:

- Lost to follow-up
- Withdrawal of consent
- The participant is not in compliance with requirements of the study, including prohibitions and restrictions
- Death

When a participant withdraws before study completion, the reason for withdrawal is to be documented in the CRF and in the source document. If the reason for withdrawal from the study is withdrawal of consent, then no additional assessments are allowed.

Withdrawal of Consent

A participant declining to return for scheduled visits does not necessarily constitute withdrawal of consent. Alternate follow-up mechanisms that the participant agreed to when signing the consent form apply (eg, consult with family members, contacting the participant's other physicians, medical records, database searches, use of locator agencies at study completion) as local regulations permit.

